9.3.2 Secondary endpoint analysis

All immunogenicity variables will be analyzed descriptively following general rules defined at the beginning of this section. In addition to the standard set of descriptive statistics, geometric mean will be reported by study visit for each population separately. For each visit after first study drug administration, the change from baseline will be analyzed descriptively.

Secondary endpoint analysis will be done on Immunogenicity Set.

9.3.3 Exploratory endpoint analysis

Number and percentage of patients with Complete Remission (CR) or Partial Response (PR) (according to RECIST 1.1) at the latest assessment during the study period out of patients with measurable disease at baseline will be reported by study visit, dose level and patient population.

The number and percentage of patients with Disease Control Rate (DCR) according to RECIST 1.1 will be reported by dose level and patient population.

In addition, best percent change from baseline in sum of target tumor measurements will be summarized and presented graphically.

Progression free survival (PFS) in patients with SD, PR, or CR at the time of first dosing according to RECIST 1.1. will be evaluated using Kaplan-Meier estimate by dose level and patient population.

Overall survival (OS) will be evaluated using Kaplan-Meier estimate by dose level and patient population.

Exploratory endpoint analysis will be done on Efficacy-evaluable Set.

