2.4 Overall Benefit-Risk Conclusion

In conclusion, this trial aims to evaluate the safety profile of the novel HER2-directed vaccine ES2B-C001 with and without adjuvant. The risks for the patients participating in the trial are considered low and it is expected that the polyclonal anti HER2 antibody response will have anticancer effects beneficial to patients participating in the trial. The overall risk-benefit-ratio of participating in this trial is judged to be favorable in patients

3 Trial Objectives and Endpoints

Table 3: Description of the objectives and endpoints of this clinical study.

Objectives	Endpoints			
Primary				
To determine the safety, tolerability, maximum tolerated dose (MTD) for ES2B-C001 alone or in combination with the adjuvant	 Nature and frequency of dose-limiting toxicities (DLTs). Incidence, nature and severity of AEs graded according to the National Cancer Institute (NCI) Common Terminology Criteria for Adverse Events (CTCAE) v5.0. Incidence, nature and severity of injection site reactions according to FDA Guidance on Toxicity Grading Scales in Vaccine Trials (FDA, 2007). 			

Clinical Study: ES2B-C001-S01 EU CT No.: 2024-516333-12-00

Objectives	Endpoints			
Secondary				
To investigate the immunogenicity of ES2B-C001 alone or in combination with the adjuvant	 Immunogenicity as humoral immune response: Total anti-HER2 Immunoglobulin titers in sera by enzyme-linked immunosorbent assay (ELISA). Isotyping of anti-HER2 Immunoglobulins in sera (e.g. IgM, IgG (IgG1-4), IgD, IgE, IgA), Optional and obligatory in the non-adjuvanted and adjuvanted treatment group, respectively. 			
Exploratory				
To determine the preliminary antitumor activity of ES2B-C001 alone or in combination with the adjuvant observed	 Percentage of patients with measurable disease at baseline achieving Complete Remission (CR) or Partial Response (PR) according to RECIST 1.1 as assessed by the investigator during routine follow up. Percentage of patients with Disease Control Rate (DCR) according to RECIST 1.1 as assessed by the investigator during routine follow up. Progression free survival (PFS) in patients with Stable Disease (SD), or PR, at the time of first dosing of ES2B-C001 alone or in combination with the adjuvant according to RECIST 1.1. Disease-free survival (DFS) in patients with CR at the time of first dosing of ES2B-C001 alone or in combination with the adjuvant according to RECIST 1.1. Overall survival (OS) 			

4 Trial Design

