8.2 Efficacy and Immunogenicity Assessments

Planned timepoints for all efficacy and/or immunogenicity assessments are provided in the SoA (Section 1.3).

Objective response rate (ORR), DCR, PFS, DFS, and OS, following RECIST 1.1 will be assessed by the investigator according to routine follow up.

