8.2.2.2 Tumor Scans During the Trial

After enrollment, tumor scans should be performed at routine follow up every 12 weeks (± 2-week window) for MBC or more frequently if clinically indicated. If a patient discontinues trial treatment, tumor scans should be performed at the time of discontinuation (± 2-week window) unless previous scans were obtained within 2 weeks of discontinuation.

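### Section 9.3.3 scores objective response at the last in-study scan, while the endpoint counts patients who achieve CR or PR, so a response that is later lost goes uncounted

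*Protocol*

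**What the plan says.** **Endpoint.** The synopsis (Section 1.1) and Table 3 (Section 3) use the same wording: "Percentage of patients with measurable disease at baseline achieving Complete Remission (CR) or Partial Response (PR) according to RECIST 1.1", as judged by the investigator in routine follow-up. Neither ties the response to a final time point. Section 8.2 names the quantity as a response rate, again with no time point: "Objective response rate (ORR), DCR, PFS, DFS, and OS, following RECIST 1.1 will be assessed by the investigator according to routine follow up".

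**Analysis.** Section 9.3.3 counts patients with CR or PR "at the latest assessment during the study period out of patients with measurable disease at baseline will be reported by study visit", and also by dose level and patient population. Later in the same section, tumour shrinkage is summarised as "best percent change from baseline in sum of target tumor measurements".

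**Scans.** Section 8.2.2.2 says "tumor scans should be performed at routine follow up every 12 weeks (± 2-week window) for MBC or more frequently if clinically indicated". It adds a scan when a patient stops trial treatment, unless one was obtained within 2 weeks. Section 8.3.5.1 puts the end-of-study visit at week 18 ± 14 days.

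**The concern.** The endpoint asks whether a patient ever reached CR or PR while followed in the study. The analysis rule asks whether the patient was still in CR or PR when last scanned. These are different quantities, and nothing else in the protocol says that a response seen earlier and then lost still counts.

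This is more than detail awaiting the SAP, because the protocol itself fixes the rule. A SAP that follows Section 9.3.3 departs from Table 3, and one that follows Table 3 departs from Section 9.3.3. Section 4.2 gives antitumour activity a use, as part of the information that should permit the design of phase 2 studies. A count that drops achieved responses would give that design a figure that is too low.

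**Working it through.** The protocol states no response rate, power or sample size for this endpoint, so there is no figure to reproduce. The check compares the two rules, then the scan timing, then the size.

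**1. The two rules on the same patient** (measurable disease at baseline, post-baseline in-study scans in order)

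| Scans | Table 3: achieved CR/PR | Section 9.3.3: CR/PR at latest |
|---|---|---|
| PR | responder | responder |
| SD, PR | responder | responder |
| PR, PD | responder | **non-responder** |
| SD, PD | non-responder | non-responder |

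**2. Direction.** Anyone in CR or PR at the latest scan has been in CR or PR at some scan. The Section 9.3.3 responders are therefore a subset of those with CR or PR at any post-baseline scan. With the same denominator, the latest-scan rate is less than or equal to the any-scan rate. This takes the endpoint as worded, with no requirement that a response be confirmed.

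**3. When the rules can differ.** A second in-study post-baseline scan is needed.

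- Routine scan k, counted from first dose (assumption; Section 8.2.2.2 gives no exact starting day): 12k ± 2 weeks. For k = 1 this is weeks 10 to 14; for k = 2, weeks 22 to 26.
- End of study: 18 ± 2 = weeks 16 to 20.
- Only the first routine scan falls inside the study period, so on routine scans alone latest and ever achieved coincide.
- Sensitivity to the starting day: if the interval ran from a screening scan at day -28, the earliest that Section 8.2.2.1 allows, the first scan would fall at 12 - 4 ± 2 = weeks 6 to 10. The next, 10 to 14 weeks later, would fall at weeks 16 to 24. That overlaps the end-of-study window only in part, and only at this extreme.
- Discontinuation scan: the treatment period is 12 weeks (synopsis) and the fifth dose is at week 12 (Section 8.3.5.2). Early stopping thus comes before about week 12, so this scan will usually be the first post-baseline scan and not one that follows a recorded response.
- What remains is mainly a clinically indicated scan after a response. Suspected progression is an obvious reason for one.

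**4. Size per patient.** One reclassified patient moves the rate by 1/n, where n is the number with measurable disease at baseline in the group tabulated. Section 4.1 gives cohort sizes of 3, 6 and 9, and Section 9.1 a maximum of 27.

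- 1/3 = 33.3 points
- 1/6 = 16.7 points
- 1/9 = 11.1 points
- 1/27 = 3.7 points

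These take the whole group as having measurable disease. If fewer do, n is smaller and the step is larger.

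**5. Expected rate (illustration; p and q are assumed and not in the protocol).** Let p be the rate of ever achieving CR or PR, and q the share of responders with a later in-study scan showing progression. The latest-scan rate is p(1 - q). For p = 0.20:

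- q = 0: 0.20
- q = 0.10: 0.18
- q = 0.25: 0.15
- q = 0.50: 0.10

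Given step 3, q may well be near the low end.

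**The case against.** The strongest reply is that the rules will rarely disagree. With one routine scan before week 18 there is usually no later scan to overturn a response, and the discontinuation scan seldom supplies one. This stands, and it sets the weight of the point. It does not remove the conflict: the clinically indicated scan is expressly allowed, and it is the scan most likely to show progression.

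It can also be said that the endpoint is exploratory and descriptive, and that escalation rests on DLTs and other safety data, with immunogenicity where available. This stands too. No decision inside the trial depends on the response rate.

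A reader might infer more than the protocol supports in four ways.

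- *Latest assessment and by study visit contradict each other.* The phrase can mean the most recent scan available at each visit, which is coherent because scans follow routine care. The wording is unclear, but a contradiction is not shown. Such a table might display an earlier response, yet it would not restore the count of patients who ever responded.
- *The latest-scan rule is faulty because the rate then depends on how often a patient is scanned.* So does an any-scan rule, since more scans give more chances to record a response. This does not separate the two.
- *Using the best value for shrinkage and the latest for response is an error in itself.* The shrinkage summary covers target lesions only, while response also depends on other and new lesions, so the two can differ under any rule. The contrast shows only that the section does not use one convention.
- *Steps of 11 to 33 points measure the expected bias.* They are 1/n for a single patient in a small group and say nothing about how often it happens.

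**Conclusion.** The point holds as a minor but real inconsistency. Section 9.3.3 analyses CR or PR at the last in-study assessment, whereas the synopsis, Table 3 and the ORR named in Section 8.2 concern patients who achieve it. Taken literally, the rule can only lower the response rate relative to CR or PR at any post-baseline assessment.

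The error is zero for every patient with a single post-baseline scan, which on the routine schedule should be most patients. Otherwise it is 1/n for each responder whose later in-study scan shows that the response is lost. The timing conclusion assumes 12-week intervals counted from first dose. An earlier starting day could bring a second routine scan inside the study period for some patients.

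The protocol does not support the reading that the reported response rate will be materially wrong or that trial decisions are at risk. The frequency of reclassification cannot be derived from it.

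**What to change.** In Section 9.3.3, replace the latest-assessment condition so that the analysis matches Table 3. For example: *the number and percentage of patients with measurable disease at baseline whose best overall response by RECIST 1.1, over all post-baseline assessments in the study period, is CR or PR, by dose level and patient population.* If response status by study visit is wanted, describe it as a separate table and say which scan represents each visit.

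The SAP should carry the same definition and state whether a response must be confirmed. With about one routine scan in the study period, a confirmation requirement could seldom be met in-study, so that choice should be deliberate.

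The cost is one sentence in the protocol and its counterpart in the SAP. No extra scans or data items are needed. Settling it before database lock avoids choosing between the two rules once the responses are known.

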	 Total anti-HER2 Immunoglobulin titers in sera by enzyme-linked immunosorbent assay (ELISA). Isotyping of anti-HER2 Immunoglobulins in sera (e.g. IgM, IgG (IgG1-4), IgD, IgE, IgA). Exploratory Endpoints: Percentage of patients with measurable disease at baseline achieving Complete Remission (CR) or Partial Response (PR) according to RECIST 1.1 as assessed by the investigator during routine follow up. Percentage of patients with Disease Control Rate (DCR) according to RECIST 1.1 as assessed by the investigator during routine follow up. Progression free survival (PFS) in patients with Stable Disease (SD), or PR, at the time of first dosing of ES2B-C001 alone or in combination with the adjuvant according to RECIST 1.1. Disease-free survival (DFS) in patients with CR at the time of first dosing of ES2B-C001 alone or in combination with the adjuvant according to RECIST 1.1. Overall survival (OS). This dose escalation part will be conducted according to an adapted 3+3
Study Period	 design. For each patient enrolled, there will be a: Screening period between 1 and 28 days prior to the first dose ES2B-C001. An out-patient treatment period of 12 weeks; Safety follow-up for ~6 weeks following the last dose of ES2B-C001. An end-of-study visit.
Study Design	The trial is a first-in-human, phase I, open-label, dose-escalating trial to assess the safety and tolerability of ES2B-C001 combined with [adjuvant] or without [adjuvant], in patients with human epidermal growth factor receptor 2 (HER2) expressing metastatic breast cancer.

Clinical Study: ES2B-C001-S01 EU CT No.: 2024-516333-12-00

Clinical Study: ES2B-C001-S01 EU CT No.: 2024-516333-12-00

The decision to escalate the dose to the next dosing cohort or initiate the expansion part will be taken by the sponsor based on the data safety monitoring board (DSMB) recommendations. The DSMB will base their recommendations on an evaluation of accumulated safety data and, if available, on immunogenicity data (antibody titers), whenever 3 patients of a specific cohort have received at least one dose, and the last patient completed the DLT observation period of 8 weeks.

Enrollment will be fully staggered in each of the populations, meaning that an observation period of 3 weeks plus 24 hours is foreseen before the second patient is dosed in one cohort. Dosing of the next subject in each cohort should ideally not take place until 1 week after the preceding patient has received the first dose.

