6.3 ES2B-C001 Dosing and Administration

In this trial ES2B-C001 should only be administered in a hospital or clinic with immediate access to equipment, medications, and appropriately qualified staff for resuscitating and stabilizing individuals in an acute emergency, along with ready availability of an intensive care unit and other hospital facilities.

Each administration of adjuvanted or non-adjuvanted ES2B-C001 will be given in the shoulder, thigh, or buttocks (alternating) by an authorized site staff proficient in English. If axillary lymph nodes have been resected on one side, the shoulder on that side should not be used for vaccination, if only 1 or 2 sentinel nodes have been removed administration may be done in the corresponding shoulder. If a region planned for administration of adjuvanted or non-adjuvanted ES2B-C001 has any clinically significant findings on day of dosing (e.g., swelling or ulceration) an alternative administration site must be chosen. Selection of region for injection should be done considering SoC treatments and allow for preferred regions for SoC to be used for that purpose (and not the vaccine).

All administrations of adjuvanted or non-adjuvanted ES2B-C001 in the ambulatory setting must be undertaken allowing for in-person monitoring and observation period of one hour following the injections.

The IMP Manual contains specific instructions for the preparation of the solutions and administration, including how to prepare the adjuvanted formulation of the final product, mixing [adjuvant] with ES2B-C001 solution.

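### The exploratory disease control rate ignores disease status at first dosing, so without a split by entry status or a reference rate it cannot be read as vaccine activity

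*Protocol*

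**What the plan says.** Table 3 (Section 3) places DCR under the exploratory objective on preliminary antitumour activity and defines it as "Percentage of patients with Disease Control Rate (DCR) according to RECIST 1.1 as assessed by the investigator during routine follow up". Section 9.3.3 gives the analysis: "The number and percentage of patients with Disease Control Rate (DCR) according to RECIST 1.1 will be reported by dose level and patient population". That section uses the Efficacy-evaluable Set, which Section 9.2 defines by one dose, one baseline tumour evaluation and one evaluation after treatment. Neither place conditions DCR on disease status at entry, and the visible text does not define patient population in those terms.

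Other endpoints do take account of the starting state:

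- The CR/PR rate in Section 9.3.3 is limited to patients with measurable disease at baseline.
- PFS in the synopsis and Table 3 is "Progression free survival (PFS) in patients with Stable Disease (SD), or PR, at the time of first dosing".
- DFS in Table 3 is "Disease-free survival (DFS) in patients with CR at the time of first dosing of ES2B-C001".
- Section 9.3.3 words PFS differently, as "Progression free survival (PFS) in patients with SD, PR, or CR at the time of first dosing", and lists no DFS analysis.

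On background treatment, Section 6.3 says: "Selection of region for injection should be done considering SoC treatments". On timing, Section 8.2.2.2 says "tumor scans should be performed at routine follow up every 12 weeks", with a window of 2 weeks either side, more often if clinically indicated, and at treatment discontinuation. Section 8.3.5.1 puts the end-of-study visit at week 18, plus or minus 14 days.

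**The concern.** On the usual reading, disease control means CR, PR or SD. A patient who enters with stable disease on other treatment and is unchanged at the next scan is counted as controlled. A patient who enters in CR and stays there is also counted, although there was no visible disease for the vaccine to act on. For such patients DCR largely restates the status at entry.

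The trial is open-label and single-arm, with 3 to 9 patients per dose level, and the protocol gives no DCR expected without the vaccine. Section 4.2 says phase 1 data, including preliminary antitumour activity, should support the design of phase 2. A DCR that background treatment alone could make high is a weak input to that, and the planned table would not let a reader see how much of it was already present at entry.

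**Working it through.** **The plan's own figures.** The protocol states no DCR, reference rate or precision to reproduce. Its sample sizes do reproduce: 3 cohorts × 3 = 9, and 3 cohorts × 9 = 27.

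**Scans within the study.** Counting from first dosing, scheduled scans fall at weeks 12 ± 2 (10 to 14) and 24 ± 2 (22 to 26). The end-of-study visit is at week 18 ± 2 (16 to 20). On that count one scheduled post-baseline scan falls in the study period.

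**Background control with no vaccine effect.** This applies to patients who are not progressing at entry. The median PFS values are assumptions, since the protocol gives none, and PFS is taken as exponential:

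P(no progression by t) = exp(−ln 2 × t / median), with 12 weeks = 12 / 4.348 = 2.76 months.

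| Assumed median PFS (months) | Scan at week 10 | Week 12 | Week 14 |
|---|---|---|---|
| 2 | 45% | 38% | 33% |
| 3 | 59% | 53% | 48% |
| 4 | 67% | 62% | 57% |
| 6 | 77% | 73% | 69% |
| 12 | 88% | 85% | 83% |

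The probability passes 50% when the median exceeds the time of the scan: about 2.8 months for week 12, 2.3 months for week 10 (10 / 4.348) and 3.2 months for week 14 (14 / 4.348).

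**If only some patients enter controlled.** Suppose half enter not progressing and the rest have 10% to 30% background control (both assumed). With a median of 4 months the overall figure is at least 0.5 × 0.62 + 0.5 × 0.10 = 36%. With a median of 12 months it is at most 0.5 × 0.853 + 0.5 × 0.30 = 58%.

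**Why the observed rate cannot be attributed.** With a 6-month median, halving the hazard raises 12-week control from 0.727 to √0.727 = 0.853. An inert vaccine on a 12-month background gives the same 85%. Without entry status, background treatment or a reference rate, the two cases look identical. Precision adds to the difficulty: the exact 95% interval is 29% to 100% for 3 of 3 controlled and 66% to 100% for 9 of 9.

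**The case against.** The strongest reply is that DCR is exploratory and descriptive. Section 9.1 states that no hypothesis is tested. Escalation and the MTD rest on DLTs and other safety data, and no activity threshold is attached to DCR. The antitumour objective also has CR/PR in measurable disease and best percent change in target lesions, which are less affected. Counting SD as control is a known limit of DCR in any single-arm trial, and Section 9.3 leaves detail to the SAP. With 3 patients per level, a split by entry status leaves very small cells. All of this stands and limits the consequence. It does not remove the point: the protocol itself fixes the denominator for DCR, and a better one is available from information that the PFS and DFS endpoints already require.

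A reader might go further and infer that most patients will count as controlled without any vaccine effect. The documents do not support that. The eligibility criteria are redacted, and the PFS and DFS wording shows only that patients in SD, PR or CR are foreseen, not how many there are. Even among those patients, a majority requires a median PFS above about 2.8 months; at 2 months the figure is 38%. The evidence for concurrent treatment is also thin: one sentence on choosing an injection site, with the concomitant-therapy restrictions in Section 6.9.2 redacted.

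A reader might likewise infer that DCR rests on a single 12-week scan. That describes the schedule only. Section 8.2.2.2 allows extra scans, and DCR is not tied to week 12.

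**Conclusion.** The point holds as a limit on interpretation. Section 9.3.3 reports DCR without regard to entry status in a trial that foresees patients already in SD, PR or CR and on other treatment. Without a split by entry status or a reference rate, the result cannot be interpreted as vaccine activity. The illustration of 38% to 85% control at 12 weeks with an inert vaccine rests on assumed medians of 2 to 12 months, exponential PFS and patients who are not progressing at entry. The true share of such patients is unknown from the documents.

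It would be too strong to say that the endpoint cannot show antitumour activity at all. It is descriptive, and other activity measures are reported beside it. This is a cheap improvement to an exploratory endpoint, with no bearing on dose escalation or the MTD.

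**What to change.** In Section 9.3.3:

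1. Report DCR by disease status at first dosing (SD, PR, and progressing if any), pooled over dose levels as well as by level.
2. Remove patients in CR at entry from the DCR denominator and report them under DFS. This requires adding the DFS analysis that Table 3 already names, and reconciling the PFS population, which includes CR in Section 9.3.3 but not in Table 3.
3. List background anticancer treatment per patient beside the result.
4. State that continued SD or PR in a patient who entered with SD or PR is not by itself evidence of antitumour activity.

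The cost is wording in the protocol and SAP. The baseline RECIST scan (Section 8.2.2.1) and concomitant medication (Section 6.9.2) are already collected, and entry status is already needed for PFS and DFS. The downside is small subgroups, which is why the pooled presentation is needed, and a less favourable headline DCR.

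### Section 9.3.3 plans PFS in patients entering with SD, PR or CR, while the synopsis and Table 3 define PFS for SD or PR and a separate DFS for CR, which has no planned analysis

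*Protocol*

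**What the plan says.** Table 3 (Section 3) lists two separate exploratory endpoints defined by disease status at entry. The first is "Progression free survival (PFS) in patients with Stable Disease (SD), or PR, at the time of first dosing of ES2B-C001"; the second is "Disease-free survival (DFS) in patients with CR at the time of first dosing of ES2B-C001". The synopsis (Section 1.1) gives the same two definitions.

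Section 8.2 keeps them apart as well: "Objective response rate (ORR), DCR, PFS, DFS, and OS, following RECIST 1.1 will be assessed" by the investigator at routine follow-up.

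The analysis section, 9.3.3, reads differently. It plans a Kaplan-Meier estimate, by dose level and patient population, of "Progression free survival (PFS) in patients with SD, PR, or CR at the time of first dosing". The only other time-to-event analysis there is for survival: "Overall survival (OS) will be evaluated using Kaplan-Meier estimate by dose level and patient population". DFS is not mentioned in 9.3.3 or anywhere else in Section 9.

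**The concern.** The protocol gives two different answers to the question of who belongs in the PFS analysis, and it defines one endpoint, DFS, for which it plans no analysis. A SAP author cannot follow both Table 3 and 9.3.3.

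This goes beyond detail that a protocol normally leaves to the SAP, such as censoring rules or table layout, because 9.3.3 itself fixes a population that departs from the endpoint definition. The opening of Section 9 describes the SAP as a fuller technical account of the analyses in that section, so the SAP's starting point is the wider PFS population and no DFS.

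At stake is the meaning of the antitumor results. Section 4.2 gives preliminary efficacy information as part of the basis for designing phase 2. A reader who takes the PFS definition from Table 3 would misread a curve that also contains patients in CR at entry. In an open-label trial, leaving the population unsettled also means that it could be chosen after outcomes are known.

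**Working it through.** No formula or stated figure is involved, so the check sets the passages side by side.

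| Place in protocol | PFS population (status at first dosing) | DFS population |
|---|---|---|
| Synopsis, Section 1.1 | SD, PR | CR |
| Section 3, Table 3 | SD, PR | CR |
| Section 8.2 | PFS listed, no population given | DFS listed separately |
| Section 9.3.3 | SD, PR, CR | none |
| Rest of Section 9 | none | none |

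1. **PFS.** {SD, PR, CR} minus {SD, PR} = {CR}. Every patient in the Table 3 PFS population is also in the 9.3.3 population; the extra members are exactly the patients for whom Table 3 provides DFS.

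2. **DFS.** It is defined twice (synopsis, Table 3) and named as assessed once (8.2), but has no analysis in Section 9.

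3. **How many patients are affected.** Let k be the number entering a dose level in CR. If k = 0, PFS is the same under both texts and DFS has no patients. If k is 1 or more, the curves are drawn on different patients. The legible text gives no value for k, and the eligibility criteria are not visible. For scale only, assume one CR patient at a dose level in which all patients are evaluable and entered with SD, PR or CR. With the cohort sizes in Section 4.1, that patient is 1/3 = 33%, 1/6 = 17% or 1/9 = 11% of those in the 9.3.3 curve. This is a share of the denominator. It does not say in which direction, or by how much, the PFS estimate would move.

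4. **How much follow-up the curves carry.** Section 8.2.2.2 schedules scans every 12 weeks with a 2-week window, and Section 8.3.5.1 puts the end-of-study visit at week 18 plus or minus 14 days. Counting from first dose, the first scheduled scan falls in weeks 10 to 14 and the second in weeks 22 to 26, after the latest end-of-study visit at week 18 + 2 = 20. Apart from extra scans for clinical need or at discontinuation, that leaves about one scheduled post-baseline scan per patient within the study.

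5. **What is not affected.** Section 9.1 states that no formal hypothesis is tested. Escalation under Sections 4.3 and 4.3.1 rests on DLTs and other safety data, with immunogenicity where available. PFS and DFS enter none of these decisions.

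**The case against.** The strongest reply is that this matters little. Both endpoints are exploratory, the trial has 9 to 27 patients, there is about one scheduled post-baseline scan each, and nothing is tested. Section 9.3 also leaves the detailed analysis to the SAP, whose authors will have Table 3 in front of them and may supply the DFS analysis. All of this bears on the size of the problem and is accepted. It does not remove the contradiction over the PFS population, which is a stated rule and not a silence. The DFS gap alone would be the weaker half of the point.

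Four stronger readings are tempting, and the documents do not support them.

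- A reader might infer that neither endpoint will be reported. PFS will be, in a wider set that contains every SD and PR patient; only DFS lacks a planned analysis. Nor can one say that the SAP will omit DFS, since the SAP is not at hand.
- A reader might infer that adding CR patients inflates PFS. The protocol does not say that CR patients are expected to do better, and such a patient can have a PFS event through recurrence or a new lesion. The direction of any shift is unknown.
- A reader might infer that restricting PFS to SD/PR would make dose levels comparable. It would not: these are small non-randomized cohorts, and the mix of SD and PR would still vary between them.
- A reader might infer that Table 3 must be right and 9.3.3 wrong. Redefining PFS to include CR and dropping DFS would reconcile the text equally well and would avoid curves based on one or two patients.

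**Conclusion.** The point holds as an internal contradiction in the current protocol. As written, PFS would not be reported in its defined population, and DFS has no planned analysis.

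The consequence is small and bounded. It concerns exploratory, descriptive reporting of antitumor activity only, and it bears on PFS only if at least one patient enters in CR, a number that cannot be judged from the legible text. MTD, dose-escalation and safety conclusions are unaffected. No numerical effect on PFS is claimed.

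The conclusion rests on the wording of the synopsis, Table 3, Section 8.2 and Section 9.3.3, which is legible in each place, and on the role that Section 9 gives the SAP. It is worth correcting because correction is cheap and because the choice of population should be settled before the outcomes are seen.

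**What to change.** Reconcile the synopsis, Table 3, Section 8.2 and Section 9.3.3 before the SAP is finalized.

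- **Preferred:** align 9.3.3 with the endpoint definitions. Estimate PFS by Kaplan-Meier in patients with SD or PR at first dosing. Add DFS for patients with CR at first dosing, by Kaplan-Meier or as a patient listing where numbers are very small. Label any curve pooling SD, PR and CR as supplementary.
- **Alternative, if the sponsor intends the pooled population:** redefine PFS in the synopsis and Table 3 as covering SD, PR and CR, and remove DFS from both and from Section 8.2.

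The cost is a few sentences in the protocol, carried into the SAP. No additional data, visits or patients are needed.
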